To assess colonization prevalence among PLWHA, we conducted an epidemiologic evaluation of MRSA among persons within the Johns Hopkins University AIDS Service (JHUAS). The study included 500 subjects (65.8 % male) along with the sexual partners of 35 subjects. The MRSA colonization prevalence was 16.8% among subjects and 37% (17/35) in their sexual partners (unpublished data). These findings demonstrate an exceptional difference in colonization prevalence in PLWHA compared to the US population¹⁰ and supports the need for further research to understand decolonization regimens that evaluate outcomes for individual decolonization only compared to the inclusion household and/or sexual partner interventions. We propose a randomized controlled trial (RCT) among 100 PLWHA (50 per arm) within the JHUAS to evaluate an individual versus household/sexual partner decolonization intervention.

2. Objectives/Aims

The specific aims of the proposed RCT are:

1. To compare a MRSA decolonization protocol for the colonized individual (index) versus the index plus their household member and/or routine sexual partner(s).
H0: Index plus household/sexual partner(s) decolonization will be associated with a lower occurrence of MRSA colonization at 6 months after completion of decolonization protocol.
2. To estimate the intervention effect size and develop an intervention fidelity assessment plan to scale the intervention into a larger multi-city R01 application.
3. To determine the molecular characteristics and antimicrobial susceptibilities of both the clinical and colonizing isolates among index patient as well as household members.

3. Background

Community-associated methicillin resistant *Staphylococcus aureus* (CA-MRSA) greatly impacts health outcomes among PLWHA. Outbreaks of CA-MRSA skin and soft tissue infections have occurred in metropolitan areas throughout the country including San Francisco¹¹, Boston¹² and Dallas¹³. These outbreaks have identified key risk differences for CA-MRSA colonization and/or infection among this population

Date: 6/10/13

Principal Investigator: [name], MPH, NP

Application Number: NA_00079147

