Dependent Variable (DV): The DV is a group of mutually exclusive, non-ordered outcomes which include: negative for *S. aureus*, positive for methicillin susceptible *S. aureus*, positive for methicillin resistant *S. aureus*.

Independent Variables: A thorough search of the available literature has been completed to develop the risk factor questionnaire designed for this study²³. The questionnaire includes: demographic data, medical history, sexual history, substance abuse history, as well as healthcare associated and community-based MRSA risk factors.

Sample Size: Based on prior studies, it appears that the probability of MRSA colonization at 6 months after decolonization ranges from 60% to 80%. Although an exact effect size is not known for individuals with household/sexual partner decolonization, we have considered both feasibility and public health importance. We believe the intervention will achieve a 50% reduction in colonization at 6 months (i.e. 30% colonization [0.30]

Date: 6/10/13

Principal Investigator: [name], MPH, NP

Application Number: NA_00079147

in the arm with individual and household/sexual partner decolonization compared to 60% [0.60] colonization in individual alone arm). **Based on these figures and an alpha of 0.05, the total sample size required to achieve approximately 80% power is 41 per arm.** We anticipate 20% attrition and will oversample by 9 subjects per arm, bringing total sample size to 50 per arm.

Statistical Analysis Plan: Demographic variables will be evaluated using chi-square and Fisher's exact testing as appropriate. Fisher's exact will also be utilized to compare proportion of persons colonized at 6 months. Multinomial logistic regression will be used to determine the odds of subsequent MRSA colonization in the two arms and to determine the magnitude of the effect size between the arms.

LIMITATIONS AND PLAN TO ADDRESS:

As with any clinical trial, this study has possible limitations:

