1. Confidentiality. In any study that includes recruitment of individuals with a specific disease process; careful discussion of these risks will be required within the informed consent process. At no time will the HIV status of the index patient be disclosed to the household member and/or sexual partner. Although persons living with HIV serve as the index patient group, the study is specific to MRSA decolonization and subsequent prevention of infection. The consent form does not mention HIV status to avoid disclosure of HIV status to potential family members.
2. Willingness of participants to participate. This study will require participants to be willing to undergo bacterial culture of private anatomical areas. In a prior JHUAS MRSA evaluation, [name] obtained these specimens in 100% of participants. The study team will work with providers within the JHUAS to recruit subjects with a history of MRSA colonization and/or infection.
3. Loss to follow-up. To ensure retention, the researchers have provided the subject with several possible methods of communication that the subject may select to best suit his/her individual needs. We will collect name, address and telephone number along with e-mail address as available for each subject. This communication will meet all necessary requirements for HIPAA to maintain confidentiality and privacy. As an incentive to encourage follow-up and participation, each subject will be offered a \$25.00 a gift card, which they will receive upon completion of each follow-up visit. We have also built into our sample size calculation a 20% oversampling in case these methods fail. Research assistants will contact the patient daily during the decolonization phase of treatment to ensure fidelity with the prescribed treatment regimen and to monitor for adverse drug reactions associated with this treatment regimen.
4. Access to all community contacts. We will be unable to test and/or evaluate all possible contacts. This may present a potential for selection bias into the study for individuals who are less sexually active or persons whose sexual partner is within the household. We will encourage all participants to provide contact details of all known consistent sexual partners, but will not seek casual sex partners.

Study Timeline:

The following 3-year study timeline provides an overview of the study preparation period, enrollment and follow-up (Table 2).

Table 2: Timeline

Year	First 6 months	Second 6 months	Year 2	Year 3

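### The 80% power at 41 per arm has no stated test or sidedness; a two-sided Fisher's exact test gives about 72% at the 40 per arm left after 20% attrition

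*Combined protocol and SAP*

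**What the plan says.** All references are to the combined protocol and SAP.

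- **Section 7, Sample Size.** The assumed 6-month colonization is 60% with individual decolonization and 30% when household members and sexual partners are included. On those rates, with "an alpha of 0.05, the total sample size required to achieve approximately 80% power is 41 per arm". No test is named, and alpha is not called one- or two-sided.
- **Section 7, Sample Size, attrition.** "We anticipate 20% attrition and will oversample by 9 subjects per arm, bringing total sample size to 50 per arm".
- **Section 7, Statistical Analysis Plan.** "Fisher's exact will also be utilized to compare proportion of persons colonized at 6 months". Sidedness is again absent. Section 4 identifies MRSA colonization at 6 months as the main outcome, so this is the main comparison.
- **Section 2, aim 1.** The hypothesis is directional: household and partner "decolonization will be associated with a lower occurrence of MRSA colonization at 6 months". It is labelled H0, and no one-sided test is declared.
- **Section 7, Limitations, item 3 (loss to follow-up).** "We have also built into our sample size calculation a 20% oversampling in case these methods fail".

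**The concern.** A power statement describes a particular test at a particular error rate. Here the sample size paragraph gives neither in full, and the test named one paragraph later is a conservative one. If the 41 came from a chi-square calculation, the planned analysis would have less power than stated. If it came from a one-sided Fisher calculation, the plan rests on a one-sided 5% error rate that it does not declare.

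Two things are at stake. The first is how a null result is read: aim 2 uses this trial to estimate an effect size for a larger application, so the real chance of missing the planned effect matters. The second is the decision rule for the main outcome. With sidedness open, some results would be significant on one reading and not on the other.

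The attrition allowance is a separate and smaller matter: the enrolled number, the attrition rate and the required evaluable number do not agree.

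**Working it through.** **Inputs (Section 7).** Rates 0.60 and 0.30; alpha 0.05; target power about 80%; 41 evaluable and 50 enrolled per arm; attrition 20%. Equal arms are assumed.

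**Step 1: reproduce 41 by normal approximation.** Two-sided, pooled variance, no continuity correction:

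n = [1.960 × √(2 × 0.45 × 0.55) + 0.842 × √(0.60 × 0.40 + 0.30 × 0.70)]² / 0.30² = 41.97, so 42 per arm, with 79.0% power at 41.

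Other two-sided variants give 40 (unpooled) and 42 (arcsine). With a continuity correction the answer is 49 two-sided and 40 one-sided. One-sided pooled gives 33. So 41 is a reasonable figure for an uncorrected two-sided calculation.

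**Step 2: exact power.** With x and y colonized in the two arms,

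power = Σ Bin(x; n, 0.60) × Bin(y; n, 0.30), summed over all (x, y) at which the test rejects.

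| Test | 40 per arm | 41 per arm |
|---|---|---|
| Fisher, two-sided 0.05 | 72.5% | 74.5% |
| Fisher, one-sided 0.05 | 79.8% | 81.3% |
| Chi-square, uncorrected, two-sided 0.05 | 79.6% | 81.3% |
| Boschloo, two-sided 0.05 | 76.4% | 77.6% |

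Both the two-sided chi-square and the one-sided Fisher test are just under 80% at 40 and above it at 41, so either could be the source of the plan's figure. Two-sided Fisher first reaches 80% at 48 per arm (78.6% at 47, 80.05% at 48).

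**Step 3: attrition.**

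- Evaluable from 50 at 20% loss: 50 × 0.80 = 40.
- Attrition that 9 extra per arm can absorb: 9 / 50 = 18%.
- Enrolment that leaves 41 after 20% loss: 41 / 0.80 = 51.25, so 52.
- Likely origin of the 50: 41 × 1.20 = 49.2, so 50. This adds 20% to 41, which is not the same as allowing for a 20% loss.

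**Step 4: consequences.** On the two-sided reading the type II error at 40 is 100% − 72.5% = 27.5%. For the decision rule, take 24/40 versus 15/40 colonized: Fisher p = 0.073 two-sided and 0.036 one-sided. Type I error is not threatened by two-sided Fisher; its maximum size is about 3.3% at 40 and 3.5% at 41.

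**Step 5: sensitivity.** Section 7 gives a 60% to 80% range for colonization after decolonization. Keeping the 50% relative reduction, two-sided Fisher at 40 per arm has:

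| Individual arm vs household arm | Power |
|---|---|
| 60% vs 30% | 72.5% |
| 65% vs 32.5% | 79.7% |
| 70% vs 35% | 85.9% |
| 80% vs 40% | 94.7% |

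**The case against.** The strongest reply is that 41 is not a miscalculation. It follows from two recognisable methods, and one of them is the planned Fisher test at one-sided 0.05, which fits the directional hypothesis. On that reading power is 81.3% at 41 and 79.8% at 40, and the word approximately covers both. This stands as far as it goes: the two-sided shortfall is conditional. But a directional hypothesis does not declare a one-sided test, nothing else in the documents does, and 72.5% is not approximately 80%.

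It can also be said that the plan powers at the least favourable end of its own control range, and that power is about 80% or better from 65% upwards. That is true, but the 80% claim is made for 60% versus 30%.

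The p-value example is a selected one. With 24/40 in the individual arm, 15 is the only count at which sidedness changes the verdict: 14 is significant both ways (two-sided p = 0.043) and 16 neither way (one-sided p = 0.059). It shows that the verdict can turn on the choice, not that it is likely to.

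Finally, the attrition slip is one participant per arm. The power change of about 2 points between 41 and 40 partly reflects the discreteness of the exact test: two-sided Fisher has 76.4% at 42 but 73.7% at 43. That is fair, and this part is minor.

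**Conclusion.** The concern holds. The stated power applies to the planned test only if alpha is one-sided 0.05, which the plan does not say. If alpha is two-sided, Fisher's exact test has 74.5% power at 41 per arm and 72.5% at the 40 expected after attrition, so the chance of missing the planned effect is about 28%. Separately, and on either reading, 50 per arm with 20% attrition leaves 40, one short of the plan's own requirement.

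These figures assume true rates of 60% and 30% and equal evaluable numbers per arm. The shortfall largely disappears if colonization in the individual arm is 65% or more with the same relative reduction. The number 41 is not itself an error; the faults are the undefined test and sidedness, the power claim that depends on them, and the attrition step. This should be fixed, with the attrition step as the lesser part.

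**What to change.** 1. In Section 7, Sample Size, state the test and sidedness behind 41. In the Statistical Analysis Plan paragraph, state whether the 6-month Fisher comparison is one- or two-sided. Do both before outcome data are seen.
2. Restate the power for that test at 40 evaluable per arm: about 72% if two-sided Fisher, about 80% if one-sided 0.05 was meant.
3. Reword the attrition sentence to say that 50 per arm leaves 40 evaluable at 20% attrition, or 41 at 18%. Bring the oversampling remark in Limitations, item 3, into line.

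Optional, and not a correction: a prespecified two-sided unconditional exact test such as Boschloo's would keep type I error at or below 5% (maximum size 4.8% at 40 per arm) and give about 76% power at 40.

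The cost is two or three sentences in the Sample Size and Statistical Analysis Plan paragraphs and one phrase in the limitations, with no added patients, visits or budget. The drawback is candour: on the two-sided reading the stated power falls below 80%, and on the one-sided reading the plan must own a less conventional error rate. The optional test is less familiar and still falls short of 80%.

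### Fisher's exact test for 6-month colonization is valid but conservative; an unconditional exact test gains about 3 to 4 points of power at exactly equal arms of 40 to 41, and about 1 to 2 points on average under simple randomization

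*Combined protocol and SAP*

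**What the plan says.** Section 7 (Study Statistics), under Statistical Analysis Plan, says of the main outcome: "Fisher's exact will also be utilized to compare proportion of persons colonized at 6 months". No other direct test of the two proportions is named. The sentence after it gives the odds of later MRSA colonization, and the size of the effect, to a multinomial logistic regression.

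Under Sample Size, the same section assumes 30% colonization in the household/partner arm "compared to 60% [0.60] colonization in individual alone arm". It then states: "an alpha of 0.05, the total sample size required to achieve approximately 80% power is 41 per arm". It does not say whether alpha is one- or two-sided, or which formula was used. On losses it says: "We anticipate 20% attrition and will oversample by 9 subjects per arm, bringing total sample size to 50 per arm".

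Section 4, under Allocation, specifies simple parallel-group randomization from computer-generated random numbers and describes no blocking. The second aim in section 2 begins: "To estimate the intervention effect size and develop an intervention fidelity assessment plan".

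**The concern.** Fisher's test conditions on the total number of colonized patients, which this design does not fix. In small samples the conditional distribution is coarse, so the test often cannot use its full 5%. Part of the permitted error rate goes unspent, and power goes with it.

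The trial expects only about 80 evaluable index patients. Each must be HIV positive, MRSA positive at screening, and have household members or a sexual partner. Changing a sentence is easier than recruiting more such patients. A result near the boundary could also turn on the choice of test: 13/40 versus 22/40 gives p = 0.071 by Fisher's test and p = 0.048 by Boschloo's.

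**Working it through.** **Inputs.** From section 7: rates 0.60 and 0.30, alpha 0.05, 41 evaluable per arm, 50 enrolled per arm, 20% attrition. Evaluable after loss: 50 × 0.80 = 40 per arm. From section 4: simple randomization. Assumption: alpha is two-sided.

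**1. The plan's own figure.** The uncorrected normal-approximation formula, with mean rate 0.45, is

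n = [1.960·√(2·0.45·0.55) + 0.842·√(0.60·0.40 + 0.30·0.70)]² / 0.30² = 41.97, or 42 per arm.

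The same approximation gives 79.0% power at 41 per arm. The stated 41 for about 80% is therefore reproduced closely, but by a formula that spends the full 5%. With a continuity correction, which approximates Fisher's test, the two-sided requirement is 49 per arm. One-sided, the requirement is 33 uncorrected and 40 corrected. The last is also near 41, so the sample size alone does not settle sidedness.

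**2. Exact comparison at equal arms.** Every 2×2 table was enumerated under two independent binomials.
- Fisher: reject when the two-sided p ≤ 0.05.
- Boschloo: use Fisher's p-value as the statistic, with the largest cut-off whose error, maximized over the common rate, is at most 0.05.
- Pooled-Z: the same construction using the pooled Z statistic.

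| Per arm | Fisher max. error | Fisher power | Boschloo max. error | Boschloo power | Gain (points) |
|---|---|---|---|---|---|
| 40 | 3.3% | 72.5% | 4.8% | 76.4% | 3.9 |
| 41 | 3.5% | 74.5% | 4.9% | 77.6% | 3.1 |
| 50 (no losses) | 3.5% | 82.9% | 4.9% | 85.5% | 2.6 |

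Pooled-Z gives the same power at these three sizes.

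**3. Why Boschloo's test cannot lose.** Rejecting at Fisher p ≤ 0.05 already keeps the error at or below 5%. Boschloo's cut-off on that same p-value is therefore at least 0.05, and its rejection region contains Fisher's.

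**4. Unequal arms.** With 80 patients analysed and a simple random split, the chance of exactly 40/40 is C(80,40)/2⁸⁰ = 8.9%; with 82 it is 8.8% for 41/41. One patient's imbalance matters. In the table, the first number is the 60% arm.

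| Split | Fisher max. error | Fisher power | Boschloo power | Pooled-Z power |
|---|---|---|---|---|
| 40/41 | 4.5% | 77.5% | 77.6% | 77.5% |
| 39/41 | 4.2% | 74.0% | 74.4% | 76.7% |
| 38/42 | 4.4% | 75.0% | 75.3% | 75.9% |

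Averaged over random splits:

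| Analysed | Fisher | Boschloo | Pooled-Z |
|---|---|---|---|
| 80 | 74.6% | 75.6% (+1.0) | 76.8% (+2.1) |
| 82 | 76.1% | 77.2% (+1.0) | 77.8% (+1.6) |

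**5. Sensitivity to sidedness.** If alpha were one-sided, power at 40 per arm would go from 79.8% to 85.6%, and at 41 from 81.3% to 86.8%. Fisher's test would then already reach about 80% at 41.

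**The case against.** Fisher's test is prespecified, familiar and holds its error below 5%. Choosing between a conditional and an unconditional exact test is partly a matter of preference, so nothing in the plan is wrong on this point. That stands.

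The equal-arm figures also flatter the change. Under simple randomization with attrition, equal arms are the exception, and one patient's imbalance nearly removes Boschloo's gain. That stands too, and it is why the average gain belongs beside the equal-arm gain. The 13/40 versus 22/40 example is a boundary table chosen at equal arms, so it shows the mechanism and not a typical result.

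A reader might infer more than the documents support in three ways.

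- **A gain of 4 to 6 points.** Two-sided, that range appears at equal arms of 43 to 49 (4.1 to 5.9 points). A one-sided alpha would give 5.8 points at 40 per arm. The plan sizes for 41 evaluable, expects 40 after losses, and does not state a one-sided test.
- **No effect size is planned because Fisher's test gives only a p-value.** The next sentence of the plan assigns effect size to the regression, on an odds scale. Boschloo's test also gives only a p-value, so this is no reason to prefer it.
- **The switch restores 80% power.** Two-sided, it gives 77.6% at 41 per arm. The stated 41 follows the uncorrected approximation and not Fisher's test; that is a separate matter, which changing the test only partly offsets.

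**Conclusion.** The point holds as a minor efficiency improvement. At exactly equal arms of 40 to 41, Fisher's test uses at most about 3.3% to 3.5% of the 5%. Boschloo's test recovers 3.9 points of power at 40 per arm and 3.1 at 41, with error at or below 5% and no possibility of lower power.

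Under the randomization the protocol describes, the realistic expectation is smaller: about 1 point with Boschloo's test and about 2 (1.6 to 2.1) with pooled-Z. Neither reaches 80% at 41 per arm.

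These figures rest on a two-sided alpha of 0.05, true rates of 60% and 30%, independent index patients, and 80 to 82 analysed.

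**What to change.** Before any 6-month results are seen, change the sentence on Fisher's test under Statistical Analysis Plan in section 7. Name one two-sided unconditional exact test, Boschloo's or pooled-Z, as the primary test of MRSA colonization at 6 months, and state the 5% level. The choice between them should be fixed in advance. Boschloo's is guaranteed never to be less powerful than Fisher's; pooled-Z has the larger average gain here. Fisher's test can stay as a sensitivity analysis.

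As a separate addition, whichever test is used, report the difference in proportions with a 95% confidence interval beside the planned regression odds. The sample size states the effect as proportions, and the second aim is to estimate its size for a larger study.

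The cost is about two sentences and no extra patients. The downside is a test that readers know less well, though standard software has it.

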The applicant proposes a prospective, randomized controlled open-label trial known as SUSTAIN, or **Stop Community MRSA Colonization among Patients**. The SUSTAIN trial will evaluate MRSA decolonization and determine differences in the prevalence of MRSA colonization (main outcome) at 6 months. Patients with a known history of MRSA colonization will be recruited from the (JHUAS). After consent and baseline MRSA screening, index subjects (50 per arm), described below, will be randomized to a standardized decolonization protocol directed at both the individual and their household and/or sexual partner(s) or a decolonization for the individual alone. Each index (i.e. person living with HIV within the Johns Hopkins Moore Clinic) will be approached for enrollment in the study. Information flyers, study rotating digital kiosk and provider referral will be used for recruitment. We will also search the Johns Hopkins Hospital Epidemiology and Infection Control (HEIC) database for known MRSA colonized individuals and contact former study participants.

SUSTAIN Standardized Decolonization Regimen (intervention):

According to the IDSA clinical practice guideline⁷, the standardized decolonization regimen for the nose and groin will include a 5-day course of nasal mupirocin calcium 2% cream applied inside the nose twice daily, plus a 4% chlorhexidine gluconate (soap) used in the shower/bath every day for 10 days^{20,19}. For individuals colonized within the throat we will add chlorhexidine gluconate oral rinse 0.12% used in a gargle and spit fashion twice daily for 7 days. A standardized educational session on use and accompanying CDC instructional frequently asked questions handout and an instructional medication sheet will be provided. For children < 7 years of age, we will provide decolonization using 4% chlorhexidine gluconate (soap) used in the shower/bath every day for 10 days. No antimicrobial cream or gargle will be utilized. If an adult household member or sexual partner is colonized at a single site, he or she will receive the soap, rinse and Mupiricin cream. If he/she is not colonized at any body site, no decolonization regimen will be provided.

Date: 6/10/13

Principal Investigator: [name], MPH, NP

Application Number: NA_00079147

ENROLLMENT:

Patient Population/Setting:

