Index patients will either 1) self refer by contacting the research assistant after seeing flyers or posted signs on the Moore Clinic revolving kiosk screen; 2) be referred from their HIV provider in clinic; or 3) be contacted by the research assistant (RA) based on known history of MRSA status from either prior participation in MRSA research studies directed by [name] or through the MRSA screening flag placed in the electronic patient record by hospital epidemiology and infection control. Screening will take place after the index patient has contacted our research team to schedule a time for an appointment within the Clinical Research Unit (CRU) or at their home based on individual preference. The PI and/or RA will provide information regarding the study, answer any questions and obtain informed consent. The PI will be available in person or via telephone to answer any questions when an RA is present for the consent. Once enrolled, the RA will assign a study identification number (SIN) to the subject. This will be the primary mode of identification throughout the study. The SIN will appear on the consent form, the questionnaire, as well as all MRSA cultures. As part of the informed consent document, the subject will receive information on how to contact the investigators to discuss culture results or any noted treatments that may be related to *S. aureus*.

During the study visit, the RA will provide the clinician with the necessary swabs for MRSA screening and will complete or assist with collection as needed. All patients presenting to the outpatient HIV clinic who are willing to undergo testing will be screened by obtaining a swab from the following anatomical sites: anterior nares, the throat, the groin/perineum, the vagina (for women) and rectum. The standardized check-list for obtaining and processing swabs has been outlined and is available for review in Appendix A.

All swabs will receive a study number pre-printed on a label. The SIN will not identify the patient's name, medical record number or other identifying information. The SIN will be used for data analysis purposes and will be recorded on the informed consent documents, the risk factor questionnaire and the surveillance swabs. Before sending the swabs, the RA will take a brief "time-out" to reassess that all paperwork is completed, swabs appropriately labeled with SIN and medical record #, as appropriate, and that all informed consent, questionnaire and swabs all contain the same SIN.

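### The between-arm effect size is assigned to a three-level multinomial model with no stated contrast, while the main outcome and sample size are MRSA yes/no; if MSSA is recorded, the arm coefficient is generally not the MRSA odds ratio

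*Combined protocol and SAP*

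**What the plan says.** Section 7 (Study Statistics) introduces the outcome with "The DV is a group of mutually exclusive, non-ordered outcomes which include" and lists three levels: no S. aureus, methicillin-susceptible S. aureus (MSSA) and methicillin-resistant S. aureus (MRSA). The Statistical Analysis Plan paragraph then states "Multinomial logistic regression will be used to determine the odds of subsequent MRSA colonization in the two arms" and gives the same model the job of quantifying the effect size. It names no reference level, no contrast and no step that turns two arm coefficients into one MRSA effect.

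Elsewhere the outcome has two levels:

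- Section 4 says the trial will "determine differences in the prevalence of MRSA colonization (main outcome) at 6 months".
- The Aim 1 hypothesis in section 2 concerns "lower occurrence of MRSA colonization at 6 months after completion of decolonization protocol".
- The sample size paragraph in section 7 says "We believe the intervention will achieve a 50% reduction in colonization at 6 months", as 30% against 60%.
- Fisher's "exact will also be utilized to compare proportion of persons colonized at 6 months". This sentence does not say MRSA, but read with the main outcome that is its natural meaning.

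Aim 2 is "To estimate the intervention effect size and develop an intervention fidelity assessment plan" for a larger application.

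On the laboratory side, Microbiological Measures in section 4 describes plating on an MRSA-selective agar, a salt broth meant to improve staphylococcal identification, and molecular typing of MRSA isolates. It writes out no step that identifies MSSA. The MRSA Screening Procedures text adds "The standardized check-list for obtaining and processing swabs has been outlined and is available for review in Appendix A". That appendix is not in the public document.

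**The concern.** In a multinomial logistic model each arm coefficient compares MRSA with one other level, not with everyone who is not MRSA positive. The plan describes the result as the odds of MRSA colonization, which is an MRSA-versus-not quantity. If MSSA is recorded, the two generally differ, and the difference depends on how MSSA is spread over the non-MRSA participants in each arm.

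What is at stake is the effect estimate that Aim 2 would carry into the design of a larger trial. An odds ratio that moves with MSSA carriage, and with a reference level chosen later, is a poor input for that.

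**Working it through.** **Inputs from section 7.** MRSA colonization at 6 months of 0.60 (individual arm, called control here) and 0.30 (household/partner arm, called intervention here); alpha 0.05, taken as two-sided because the plan does not say; about 80% power; 41 per arm. The documents give no MSSA rates, so every MSSA rate below is an assumption.

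**The plan's own figure.** The normal-approximation formula with pooled variance is n = [1.96 × √(2 × 0.45 × 0.55) + 0.842 × √(0.6 × 0.4 + 0.3 × 0.7)]² / 0.30², which gives 42 per arm. At 41 per arm the same approximation gives 79.0% power. The stated 41 for approximately 80% is reproduced, and it is a calculation for a yes/no outcome.

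**Target odds ratio, MRSA versus not.** (0.30/0.70)/(0.60/0.40) = 0.286. With 41 per arm the standard error of the log odds ratio is √(1/12.3 + 1/28.7 + 1/24.6 + 1/16.4) = 0.467, so the expected 95% CI is 0.114 to 0.713.

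**If MSSA is not recorded.** The outcome has two levels, the multinomial model is binary logistic regression, and it returns 0.286. Only the definition of the dependent variable is then out of line.

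**If MSSA is recorded.** Let s be the MSSA share of non-MRSA participants in an arm. The negative proportions are 0.70 × (1 − s_int) and 0.40 × (1 − s_ctl), so

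MRSA-versus-negative OR = 0.286 × (1 − s_ctl)/(1 − s_int).

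This equals 0.286 only when s is the same in both arms. Equal MSSA percentages of all participants do not meet that condition, because the non-MRSA groups differ in size (40% and 70%).

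| Assumed MSSA, control/intervention (% of all) | s_ctl, s_int | MRSA vs negative OR | Expected 95% CI, 41 per arm |
|---|---|---|---|
| 10 / 17.5 | 0.25, 0.25 | 0.286 | 0.107 to 0.761 |
| 10 / 10 | 0.25, 0.143 | 0.25 | 0.095 to 0.658 |
| 20 / 20 | 0.50, 0.286 | 0.20 | 0.069 to 0.577 |
| 10 / 30 | 0.25, 0.429 | 0.375 | 0.137 to 1.027 |

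The second row, for instance, is (0.30/0.60)/(0.60/0.30) = 0.25. The gap is zero at equal shares and can go either way otherwise. Even at equal shares the interval is wider than the binary one.

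**Check by fitting.** With 1,000 per arm and counts (negative, MSSA, MRSA) of 300, 100, 600 in control and 500, 200, 300 in intervention, a multinomial fit gave 0.30 for MRSA versus negative. Binary logistic regression on the same data gave 0.286.

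**The case against.** The strongest reply is that the plan never says it will report a raw coefficient. It speaks of the odds of MRSA in the two arms. A multinomial model with arm as its only term reproduces the observed proportions in each arm, so the MRSA-versus-not odds and their ratio can be read off. That is correct. What remains is that the plan does not state this step, and it names this model as the source of the effect size.

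Second, the numerical effect arises only if MSSA is identified, and no available text describes such a step. This also stands. A reader might go further and infer that the laboratory method cannot fill the MSSA level. The documents do not support that: the salt broth is there to improve staphylococcal identification, and the check-list in Appendix A cannot be seen. The supportable statement is that no MSSA step is described and the matter is unclear.

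Third, a reader might point to MSSA as the base level, where the last three table rows would give (0.30/m_int)/(0.60/m_ctl), with m the MSSA proportion in each arm: 0.50, 0.50 and 0.167. Nothing in the plan suggests that choice. The negative level is listed first and is the natural comparator for colonization, so these figures should not be used to gauge the problem.

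Fourth, the two proportions compared by Fisher's test already contain the yes/no effect, so Aim 2 would not be left without one. True, but the plan assigns the effect size to the other model.

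**Conclusion.** The point holds as a minor mismatch between a stated model and the quantity it is said to estimate. If MSSA is not recorded, there is no numerical error. If it is recorded and the MRSA-versus-negative coefficient is reported without conversion, the odds ratio departs from 0.286 unless MSSA shares are equal; it is 0.20 to 0.375 in the unequal-share examples. Those examples rest on assumed MSSA rates, illustrate direction and scale, and are not a forecast. All of them lie within the binary estimate's own expected interval of 0.114 to 0.713.

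A reader might infer that the trial's main comparison is compromised or that a wrong effect size will be published. Neither follows. Fisher's test and the 41 per arm do not use the multinomial model, and the plan leaves room for a correct conversion. The consequence is confined to the Aim 2 effect estimate.

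**What to change.** Define the effect-size outcome as MRSA positive versus not at 6 months, and estimate it by binary logistic regression on arm with a 95% CI. The risk difference or risk ratio could be added, since the sample size expresses its effect as a reduction in the proportion colonized; this is optional. State in the Fisher sentence that colonized means MRSA colonized.

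Keep the three-level multinomial model as a secondary analysis only if the protocol states how MSSA is identified and which level is the reference. Otherwise remove the MSSA level from the dependent variable.

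The main change is wording in section 7 and adds no participants, visits or swabs. Keeping the secondary model requires the MSSA identification step to be stated in the laboratory procedure, or added if there is none.
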